1.3 Correlative Studies

All correlative studies will be collected under HRPO# 201011766 (“Tissue Acquisition for Analysis of Genetic Progression Factors in Hematologic Diseases”) that all patients will be concurrently enrolled in. The goals of the correlative studies include:

1. To correlate patient-specific mutations with response to decitabine.
We will perform exome sequencing of each patient’s pre-study bone marrow sample and skin sample. We will determine AML/MDS-associated variants found in the bone marrow, but not skin sample. We will correlate the presence of mutations with response (especially mutations in *DNMT3A*, *IDH1*, *IDH2*, and *TET2*). This study is powered to identify mutations with >80% sensitivity to predict decitabine response if used as a clinical assay.
2. To correlate the velocity and depth of response with response to decitabine.
We will assess tumor burden by allele frequency of patient-specific mutations in bone marrow samples collected pre study, Cycle 1 Day 10±1, Cycle 1 Day 28±4, and Cycle 2 Day 28±4. We will assess mutations in at least 24 recurrently mutated genes (including, but not limited to: *FLT3*, *DNMT3A*, *NPM1*, *TET2*, *WT1*, *IDH1*, *IDH2*, *RUNX1*, *NRAS*, *TP53*, *U2AF1*, *KRAS*, *PHF6*, *MSTP9*, *PTPN11*, *KIT*, *SMC3*, *PRUNE2*, *ETV6*, *CEBPA*, *SMC1A*, *ASXL1*, *STAG2*, *RAD21*) as well as all patient-specific mutations discovered during exome sequencing. The leukemic allele frequency will be measured using the Illumina MySeq or HiSeq platform using DNA capture by gene specific biotinylated-oligonucleotides. Patient bone marrow samples will be assessed pre-study, Cycle 1 Day 10 ± 1, Cycle 1 Day 28 ± 4, and Cycle 2 Day 28 ± 4 and compared with patient specific skin samples (normal control). The velocity of response will be calculated as the natural log rate of patient-specific mutation allele frequency clearance. Depth of response will be defined as the lowest patient-specific mutation

allele frequency in a bone marrow sample. The velocity and depth of tumor response will be correlated to:

- Achievement of clinical CR,
- Time to best response,
- Mutational status,
- Time to disease progression.

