9.4 Other Secondary Efficacy Measures

9.4.1 Treatment Failure, Overall Survival and Event-free Survival

Treatment failure is defined as failure to achieve a complete or partial remission following 4 cycles of therapy.

Overall survival is defined as the date of first dose of study drug to the date of death from any cause. Patients still alive at the time of the final analysis will be right-censored.

Event-free survival is defined as the interval from the date of first dose of study drug to date of treatment failure, recurrence, death due to any cause, or loss to follow up.

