14.2.3 Secondary Endpoint Analyses

The overall response rate (CR/CRi/PR) and complete response rate (CR/CRi) will be compared with historical controls[2], and the 95% confidence intervals will be provided.

The rate of patient specific mutation clearance after 10, 28, and 56 days of therapy will be determined using an Illumina based platform. We will compare the rate of mutation clearance between the patients who achieve a CR/CRi after 4 cycles and those who do not. We anticipate that we will identify between 6 and 25 exonic SNVs per case (the range obtained with >200 AML samples sequenced to date with whole genome or exome sequencing), and that the expected 95% confidence interval of the mean variant allele frequency will be $\pm 2.56\%$ and $\pm 1.25\%$,

respectively, if we assume an anticipated standard deviation of 3.2% within the same clone. The change of tumor burden over time and its association with clinical response will be assessed using 2-way ANOVA for repeated measurement data, followed by the ad-hoc multiple comparisons for between-group differences (e.g., responders vs. non-responders) at given time points as well as the between-time differences within each group. The resultant critical P values will also be corrected using permutation analysis for multiple testing.

The percent decrease in bone marrow methylcytosine will be calculated on day 10 ± 1 . We will compare this reduction with previously published data and between the patients who achieve CR/CRi and those who do not. The correlation of peak plasma levels of decitabine with response will be assessed using 2-sample t-test or Mann-Whitney non-parametric rank-sum test as appropriate. The change of total bone marrow DNA methylcytosine from baseline and its association with both steady-state plasma drug levels and response will be assessed using 2-way ANOVA for repeated measurement data, followed by the ad-hoc multiple comparisons for between-group differences (e.g., responders vs. non-responders) and between-time differences. Similar analyses will be performed for the correlation of expression profiles and SNP analysis with pharmacokinetic data.

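### Depth of mutation clearance is to be correlated with time to progression with no landmark or fixed sample window, so a false link between deeper clearance and later progression is not prevented

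*Combined protocol and SAP*

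**What the plan says.** In the combined protocol and SAP, Section 1.3, item 2, tumour burden is the VAF of patient-specific mutations in "bone marrow samples collected pre study, Cycle 1 Day 10±1, Cycle 1 Day 28±4, and Cycle 2 Day 28±4". With no cycle delay the last of these falls at about day 28 + 28 = 56. Two summaries are formed. For velocity: "The velocity of response will be calculated as the natural log rate of patient-specific mutation allele frequency clearance". For depth: "Depth of response will be defined as the lowest patient-specific mutation" allele frequency found in a marrow sample. No window, minimum number of samples or rule for missing samples is given. "The velocity and depth of tumor response will be correlated to" four items, the last being "Time to disease progression".

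Section 14.2.3 repeats the timing ("The rate of patient specific mutation clearance after 10, 28, and 56 days of therapy will be determined using an Illumina based platform") but tests something else: "We will compare the rate of mutation clearance between the patients who achieve a CR/CRi after 4 cycles and those who do not". Its model is a repeated-measures ANOVA against response. Times to relapse and death are only listed by patient.

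Section 9.4.1 starts overall survival at first dose and does the same for event-free survival ("Event-free survival is defined as the interval from the date of first dose of study drug to date of treatment failure" or one of its other events). Time to progression has no stated origin, event rule, censoring rule or model. The efficacy-evaluable set in Section 14.1 needs only one cycle, so it does not act as a landmark at the end of Cycle 2.

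**The concern.** A minimum over more samples, and over later samples when VAF is falling, tends to be lower. The later marrows exist only for patients still being sampled. Section 5.3 ends treatment at progression or death, so someone who fails on day 40 may have a depth based on the pre-study, day 10 and day 28 marrows, while a longer survivor's depth also draws on day 56. Part of the outcome then decides how the predictor is measured. The resulting error favours the hoped-for finding that deep early clearance marks durable control.

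The drop-out allowance does not cover this loss. Section 14.2.2 supports a figure of 20% or less by saying that the molecular data are in hand within 30 days of enrolment, and the Cycle 2 marrow comes later than that.

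**Working it through.** **The plan's own figures.** None is stated for the correlation with time to progression. The nearest, for the clearance measure, reproduce. The confidence half-widths are 1.96 × 3.2/√6 = 2.56 and 1.96 × 3.2/√25 = 1.25. Two-sample t-test power is 99.8% (6 variants, 10-point difference) and 98.6% (3 variants, 15-point difference) at SD 3.2, and 91.2% and 82.8% at SD 4.7. The plan states >99%, >98%, 91% and 82%.

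**Simulation A: no true association.**

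- From the documents: samples at days 0, 10, 28 and 56; 100 evaluable patients (45 + 55, Section 14.2.3); two-sided alpha 0.05; two years of follow-up, simplified to 730 days from first dose.
- Assumed: exponential progression time with median 90, 180 or 365 days; start at VAF 40%; mean slope of ln(VAF) −0.03, −0.015 or 0 per day (between-patient SD 0.03); noise SD 0.3 on the log scale. At −0.03 the central path is 40·exp(−0.03t), or 29.6%, 17.3% and 7.5% at days 10, 28 and 56.
- Method: samples after progression are lost. Depth is the minimum of those left and velocity is their least-squares slope. Cox score test, time from first dose, 4,000 runs per setting.
- Share progressing before day 56: 1 − 2^(−56/median).
- Share left at a day-60 landmark (day 56 plus the 4-day window): 2^(−60/median).

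| Median progression (days) | 90 | 180 | 365 |
|---|---|---|---|
| Progressing before day 56 | 35% | 19% | 10% |
| Depth, false positives, slope −0.03 | 80.7% | 36.4% | 16.0% |
| Depth, slope −0.015 | 55.0% | 21.6% | 10.8% |
| Depth, slope 0 | 32.1% | 12.7% | 7.4% |
| Left at day-60 landmark, of 100 | 63 | 79 | 89 |

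On average the error runs one way in every cell: lower VAF is linked to later progression. Other results:

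- Velocity: 6.5% to 11.9% using all available samples, with mean z of 0.0 to 0.4; 5.0% to 6.6% among patients who have the Cycle 2 marrow.
- Nobody progressing before day 56: depth 4.7% to 5.9%.
- Day-60 landmark, time counted from it: depth 4.8% to 6.4%, velocity 4.5% to 6.4%.
- Section 8.0 also collects correlative marrows in Cycles 4 and 6. If these enter the minimum (slope −0.03), depth gives 99.9%, 96.3% and 72.1%.

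**Simulation B: the sampling rule.** Assumed mean VAF path 40, 35, 29, 21%; 100 patients; Spearman test of depth against progression time; 1,000 runs. Moderate spread means a baseline SD of 10 points and an SD of 1 for the log-decline multiplier, with noise of 3.2 points. Low spread means 5 and 0.3. Each cell gives false positives at medians of 90/150/210/300 days.

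| Rule | Moderate spread | Low spread |
|---|---|---|
| Samples after progression lost | 91/62/43/25% | 100/99/90/65% |
| Progression dated at the scheduled marrow, that sample counted | 23/12/10/7% | 80/45/30/18% |
| Everyone sampled through Cycle 2 | 5/5/5/6% | 6/5/5/5% |

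**The case against.** The strongest reply is that the protocol's own schedule limits the loss of samples. AML progression rests mainly on marrow blasts (Section 9.1), and disease is assessed at the same Day 28 marrows that supply the VAF (Sections 5.2.8 and 9.3). A progression found at Cycle 2 Day 28 therefore still yields that sample. The study schema, in the bound copies that show it, ties removal to progression after two cycles, which suggests that many early progressors reach that marrow. This stands, and simulation B shows how much it matters: at moderate spread and a 90-day median, 91% falls to 23%. It does not remove the problem, because early deaths, off-schedule progression and stopping under Section 5.3 still lose samples. At low spread the scheduled-marrow rule still gives 18% to 80%.

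A second reply is that the analysis carries little weight. The primary objective concerns mutations and response. The secondary objective in Section 2.2 links clearance to overall response, and Section 14.2.3 tests it only against response. Progression is the last bullet in a correlative section, with no test or power claim. That is right, and it limits the importance of the point. It does not make the depth rule sound for the correlation that Section 1.3 says will be done.

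**Conclusion.** The point holds for depth. Using each patient's lowest available VAF, with time from first dose, can produce a false link between deep clearance and late progression, and nothing in the plan prevents it. With some VAF decline and samples through Cycle 2, the false-positive rate runs from about 7% to over 90%. It depends on progression times, the rate of decline, between-patient spread and whether the progression-visit marrow counts, none of which the documents give. It is about nominal if everyone is sampled through Cycle 2.

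A reader might infer more, in three ways:

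- **That the plan prescribes the bias, so an artefact is certain.** It does not. Origin, model and handling of early failures are unstated, and the first-dose origin is borrowed from Section 9.4.1. Nor must VAF fall in every patient.
- **That velocity is equally affected.** A log rate does not drop merely because more samples exist. The modest inflation comes mainly from noisier slopes in early progressors, so velocity chiefly needs a fixed window.
- **That a central claim of the trial is at risk.** The primary mutation-response analysis is untouched.

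This is a cheap improvement to one correlative analysis.

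**What to change.** In Sections 1.3 and 14.2.3:

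1. Define time to progression: origin, event, how death without progression is treated, and censoring.
2. Compute depth and velocity only from samples through Cycle 2 Day 28, and state how a missing marrow is handled.
3. Analyse both against time to progression from a landmark at the Cycle 2 Day 28 marrow, in patients alive and progression-free then, with time counted from it. A progression found on that marrow counts as before the landmark. Alternatively, enter VAF as a time-dependent covariate from first dose.
4. Report how many patients are excluded and why.

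Merely requiring a Cycle 2 sample is a half-measure: with time from first dose it still credits each patient with about 56 event-free days.

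The cost is wording; no visit or sample changes. Patients who fail before about day 56 leave this one analysis, and its result applies only to those progression-free at the end of Cycle 2. The retained numbers in the first table rest on assumed medians.

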Because all patient-specific exome-discovered mutations will be assessed a second time in the primary bone marrow sample as well as the Cycle 1 Day 10 \pm 1, Cycle 1 Day 28 \pm 4, and Cycle 2 Day 28 \pm 4 bone marrow samples, this study will also serve to validate all exome-discovered mutations. This is important, because exome sequencing is associated with a 20-50% false-discovery rate depending on type I error tolerated (mutation-calling algorithms are typically set for greater sensitivity than specificity). Thus, many mutations discovered during exome sequencing are incorrect. This second analysis of these mutations will serve to exclude these false positive calls.

3. To correlate the bone marrow expression profile from pre-study and Cycle 1 Day 10 \pm 1 with response to decitabine.

We will correlate expression signatures, and changes in expression signatures, with:

- Achievement of clinical CR,
- Mutation status.

4. To correlate the extent of bone marrow DNA hypomethylation on Cycle 1 Day 10 \pm 1 with response to decitabine.

We will assess the percent reduction in bone marrow methylcytosine content using LC-MS. Patients will be evaluated pre-study and Cycle 1 Day 10 \pm 1. The change in DNA methylcytosine content will be correlated to:

- Achievement of clinical CR,
- Change in expression signature.

This will determine whether inadequate blast exposure to decitabine correlates with drug resistance.

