3.0 PATIENT SELECTION

3.1 Inclusion Criteria

All of the following:

- Patient must have non-M3 AML or MDS
- An adverse risk karyotype defined by:
 - Complex karyotype by cytogenetics, or
 - Deletion of all or part of chromosome 5, 7, 12, or 17 defined by FISH or cytogenetics, or
 - Somatic TP53 mutation

All of the following:

1. Patient must have an ECOG performance status ≤ 2 .
2. Patient must have $>10\%$ disease burden measured by cytomorphology, flow cytometry, or cytogenetics.
3. Patient must have peripheral white blood cell count $\leq 50,000/\text{mcl}$.
4. Patient must have adequate organ function, defined as:
 - a. Total bilirubin $\leq 1.5 \times \text{ULN}$
 - b. AST/ALT $\leq 2.5 \times \text{ULN}$
 - c. Serum creatinine $\leq 2.0 \times \text{ULN}$
5. Patient must have undergone ≤ 2 cycles of prior hypomethylating agent (decitabine or azacitidine).
6. Patient must be enrolled in HRPO# 201011766 (“Tissue Acquisition for Analysis of Genetic Progression Factors in Hematologic Diseases”).
7. Patient must be ≥ 18 years of age.
8. Patient must be able to understand and willing to sign an IRB-approved written informed consent document.

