Statistical power justification. A power analysis was performed using two-sample t-test for between-group difference and paired t-test for the change over time. For tumor clearance, this will provide $> 99\%$ power to detect a 10% difference in the means at two separate time points for clones with 6 or more variants, and $> 98\%$ power to detect a 15% difference if there are 3 or more variants per clone with $\alpha = 0.05$ (power will decrease to 91% and 82%, respectively, in cases where the standard deviation is 4.7%, the maximum we have observed thus far). For pharmacologic correlations, we anticipate 85% power to determine a 25 ng/ml difference between the average C_{\max} of 45 evaluable responders and 55 evaluable non-responders with an anticipated average C_{\max} of 70 ng/ml and a standard deviation of 40 ng/ml within the entire cohort, and with $\alpha = 0.05$. [22] We believe a less significant difference would not be sufficient to warrant application in clinical decision making (i.e. whether to continue therapy for more than 1 cycle). We anticipate 99% power to determine a difference of 20% in the reduction of bone marrow methylcytosine between 45 evaluable responders and 55 evaluable non-responders with an expected standard deviation of 15% and $\alpha = 0.05$. [28, 66-68] The difference in methylcytosine reduction previously observed was 30% between patients achieving CR/PR and those with only hematologic improvement. [28]

Time to relapse and time to death will also be listed for each patient.

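### The fall in total marrow methylcytosine is read as blast exposure to decitabine, but the planned responder comparison makes no allowance for disease-cell fraction

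*Combined protocol and SAP*

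**What the plan says.** All references are to the combined protocol and SAP. Section 1.3 item 4 defines the measure: "We will assess the percent reduction in bone marrow methylcytosine content using LC-MS", taken pre-study and at Cycle 1 Day 10. It then gives the reading: "This will determine whether inadequate blast exposure to decitabine correlates with drug resistance".

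Section 14.2.3 names the compartment as all marrow DNA ("The change of total bone marrow DNA methylcytosine from baseline") and sets the contrast "between the patients who achieve CR/CRi and those who do not", with repeated-measures ANOVA for the change over time. The power statement in the same section is "We anticipate 99% power to determine a difference of 20% in the reduction of bone marrow methylcytosine". Its inputs are group sizes of 45 (responders) and 55 (non-responders), an SD of 15% and alpha 0.05, in a two-sample t-test.

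No blast sorting or enrichment is described, and no covariate is named for this analysis. The logistic regression in Section 14.2.2 belongs to the primary analysis, names no blast or burden variable, and is not carried over. Eligibility in Section 3.1 asks only for more than 10% "disease burden measured by cytomorphology, flow cytometry, or cytogenetics".

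**The concern.** A single methylcytosine value for a marrow sample averages over disease cells and everything else. Nothing in the plan ensures that the mix is similar in the two response groups, and several features allow it to differ:

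- Disease burden may lie anywhere above 10%, by any one of three methods.
- AML and MDS are pooled. Section 1.1 notes that MDS is clonal even with no morphologic blasts, and Section 9.2 foresees MDS baseline blasts below 5%.
- CRi is defined only for AML (Section 9.1), and Marrow CR for MDS (Section 9.2) is not named in CR/CRi. MDS marrow responders could therefore be counted as non-responders.
- Section 14.2.3 itself compares mutation clearance at Day 10 between CR/CRi patients and others, so the plan already treats Day 10 burden as possibly related to response.

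At stake is what may be concluded. A significant difference could reflect burden and not exposure, and a null result could hide a real exposure difference.

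**Working it through.** **Inputs from Section 14.2.3.** Groups of 45 and 55; SD 15; target difference 20; alpha 0.05. I take the test as two-sided, the percentages as percentage points of reduction, and the SD as within-group.

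**Step 1, the plan's own figure.** SE = 15 × √(1/45 + 1/55) = 3.015. The standardised difference is 20/3.015 = 6.63. The two-sided t-test with 98 degrees of freedom has power above 99.99%, so the stated 99% is met with room to spare.

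**Step 2, what else the comparison detects.** The smallest significant difference is 1.984 × 3.015 = 5.98, about 6.0 points. The difference with 80% power is (1.960 + 0.842) × 3.015 = 8.4 points. A true artefact of 6.0 points has about a 50% chance of reaching significance.

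**Step 3, artefact with identical blast exposure.** Let f be the disease fraction, D the percent loss in disease cells and N the loss in other cells, the same for every patient. Marrow fall = f × D + (1 − f) × N. The difference between group means is then (difference in mean f) × (D − N). The documents give neither D nor N, so both are assumptions. The table shows the difference in mean disease fraction, in points, needed for each size of artefact.

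| D − N (points) | 6.0-point artefact | 8.4-point artefact | 20-point artefact |
|---|---|---|---|
| 60 | 10 | 14 | 33 |
| 40 | 15 | 21 | 50 |
| 35 (40% vs 5%) | 17 | 24 | 57 |
| 20 (40% vs 20%) | 30 | 42 | 100 |
| 10 (40% vs 30%) | 60 | 84 | not possible |

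For example, 6.0/0.35 = 17, 8.4/0.35 = 24 and 20/0.35 = 57. As D − N goes to zero, so does the artefact.

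**Step 4, direction.** Step 3 holds f fixed between the two samples. If f changes and all cells start with equal methylcytosine, the Day 10 fraction governs the fall. Responders who clear early then show a smaller marrow fall, which masks a true responder excess. If disease cells start with r times the methylcytosine of other cells, clearance alone changes the marrow value, with no demethylation at all: reduction = 1 − [1 + f1(r − 1)]/[1 + f0(r − 1)], where f0 and f1 are the pre-study and Day 10 fractions. Take responders going from 60% to 10% and non-responders from 60% to 50%. The gap is 0 points at r = 1.0, 10 at 1.3, 15 at 1.5 and 25 at 2.0, and its sign reverses below 1. The documents give neither r nor these fractions, so the direction and size are open.

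**The case against.** The strongest reply is that the secondary objective in Section 2.2 item 3 concerns the decrease in bone marrow methylcytosine, not in blasts, and the planned contrast answers exactly that. This stands. The fault lies in one interpretive sentence in Section 1.3 and in the missing adjustment, not in the objective.

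Second, sample handling may be described in the separate tissue-acquisition protocol under which marrow is collected, and total may mean global methylcytosine and not unsorted cells. That cannot be excluded from these documents. If enrichment is done, the plan should say so; as written, the blast reading has no stated support.

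Third, the size rests on cell-level losses that the documents do not give. This also stands, and it is why the table runs down to contrasts at which the artefact nearly disappears.

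Fourth, Day 10 disease fraction is measured after treatment and partly reflects response, so adjusting for it may remove some of the association under study. This is correct and limits the remedy.

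A reader might go further and infer that disease fraction alone would produce the 20-point difference in the power statement. Two individual marrows can differ that much: with losses of 40% and 5%, a marrow with 80% disease falls 33.0 points and one with 15% falls 10.25, a gap of 22.75. The power statement, however, concerns group means, which at that contrast would need disease fractions 57 points apart. The clearance route in Step 4 passes 20 points only with a large assumed excess of methylcytosine in disease cells and fast clearance confined to responders. The documents support neither.

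**Conclusion.** The concern holds in limited form. The planned comparison cannot by itself show whether blasts were inadequately exposed, because it mixes any drug effect with the share of disease cells in the marrow. A modest imbalance is enough to matter: under the assumed 35-point contrast, mean disease fractions about 17 points apart reach the significance threshold, and about 24 points apart give an 80% chance of a significant result, with identical exposure in every blast. The bias may run either way, so a null result is affected too.

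The conclusion that item 4 overreaches depends only on the two compartments possibly differing in methylcytosine loss or content. The sizes depend on the assumed contrast, the two-sided test and a within-group SD of 15. It would be wrong to conclude that the secondary objective goes unanswered. This is a correlative secondary analysis, and the Table 3 power calculation for the primary endpoint is unaffected.

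**What to change.** In Section 14.2.3, keep the unadjusted CR/CRi comparison and add one adjusted for pre-study disease fraction and for AML versus MDS. Prespecify a single measure of disease fraction. Mutation allele frequency is the better choice, because blast percent can be near zero in clonal MDS. Report a further model with Cycle 1 Day 10 allele frequency as a sensitivity analysis only, noting that it is post-treatment and may remove part of the drug-response association.

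In Section 1.3 item 4, replace the closing sentence with a statement that the result describes change in total marrow methylcytosine and does not by itself determine blast exposure. This limit applies to the adjusted result as well, since a covariate does not recover the loss per blast when that loss varies between patients.

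Allele frequency is already planned at both times (Section 1.3 item 2), so no sample or assay is added. The cost is slightly wider intervals and the loss of patients without allele-frequency data from the adjusted analyses.
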